4.2. Patient selection

4.2.1. Inclusion criteria

Plasma donors may be selected from among patients already discharged for COVID-19 in the centres participating in the study (who have not received plasma), as well as by volunteers who meet the requirements for inclusion and non-exclusion, who wish to donate and go to HUSLL or the blood and tissue bank of the Balearic Islands.

The study sample for both the intervention and control group will be extracted from patients who are positive in the real time-polymerase chain reaction (RT-PCR) test for the detection of COVID-19, in any of the participating centres (admitted to the plant or ICU), and who meet the inclusion and non-exclusion criteria, and voluntarily wish to participate, after being informed with the Patient Information Sheet (HIP), and have signed the informed consent (IC).

Both donors and study subjects will be provided with the specific HIP and IQ. Each participating centre will sign a participation agreement, confidentiality commitment and transfer of study results for further analysis, following the usual logistics guidelines of multicentre studies.

1. Below are the inclusion criteria:

For the receiver:

A. Recipients hospitalized in COVID-19 floor:

1. Ability to understand the HIP and sign the IQ of the study.
2. Age greater than or equal to 18 years, male or female.
3. Patient hospitalized in COVID-19 floor (or equivalent areas in each centre) with COVID-19 diagnosis by PCR in nasopharyngeal smear or in any other biological sample.

4. Presence of respiratory symptoms and / or fever associated with COVID-19, with time of evolution of the clinic by COVID-19 equal to or less than 7 days (being day 1 the day of onset of symptoms and including day 7).
5. Presence of pneumonia in chest x-ray and/or $\text{SatO}_2 < 94\%$ aa.
6. Sequential Organ Failure Assessment score (SOFA) ≤ 6 .
7. Accept the condition of complying with the procedures established in the protocol.
8. That you will remain admitted at least 5 days at the discretion of the clinician, in order to perform the procedures correctly.

B. Recipients hospitalized in ICU:

1. Ability to understand the HIP and sign the IQ of the study. **In case of impossibility of signing IC (e.g., intubated patients) the oral IC will be accepted.**
2. Age greater than or equal to 18 years, male or female.
3. Patient hospitalized in ICU with COVID-19 diagnosis by PCR in nasopharyngeal smear or in any other biological sample.
4. Presence of respiratory symptoms and / or fever associated with COVID-19, with time of evolution of the clinic by COVID-19 equal to or less than 7 days (being day 1 the day of onset of symptoms).
5. Sequential Organ Failure Assessment score (SOFA) > 6 .
6. Accept the condition of complying with the procedures established in the protocol.
7. In addition, for ICU patients, the criteria for admission to the ICU that has been given by the Ministry of Health and the Spanish Society of Intensive Care Medicine will be considered (**updated to the current situation**). A summary is attached to the following table, and more information is added in Annex IX (also available www.semicyuc.org · www.fepimeti.org · www.seeeiuc.org).

MAJOR CRITERIA (1 criterion necessary)
Septic shock with the need for vasoactive drugs
Respiratory failure requiring mechanical ventilation
MINOR CRITERIA (3 or more criteria)
Respiratory rate > 30 breaths/minute with conventional oxygen therapy
$\text{Pao}_2/\text{FiO}_2 < 250$ with conventional oxygen therapy
Bilateral infiltrates
Altered level of consciousness
Elevation of urea ($< 20\text{mg/DL}$)

Leukopenia (<4000 cells/ml) and lymphopenia
Thrombocytopenia (<100000/ml)
Hypothermia (<36°C)
Hypotension requiring aggressive resuscitation with fluids
D-dimer > 1 µg/L

In case of overflow situation, the following triage tool will also be considered, based on the use of the SOFA.

Colour Code	Initial Assessment	48 hour Assessment	120 hour Assessment	Priority/Action
Blue	Exclusion Criteria* or SOFA > 11*	Exclusion Criteria Or SOFA > 11 Or SOFA 8 – 11 no	Exclusion Criteria* or SOFA > 11* or SOFA < 8 no	Medical Mgmt +/- Palliate & d/c from critical care
Red	SOFA 7 or Single Organ Failure	SOFA score < 11 and decreasing	SOFA score < 11 and decreasing progressively	Highest
Yellow	SOFA 8 – 11	SOFA < 8 no	SOFA < 8 with < 3 point decrease in past 72h	Intermediate
Green	No significant organ failure	No longer ventilator dependant	No longer ventilator dependant	Defer or d/c, reassess as needed

Patients who do not meet the inclusion criteria may remain in conventional hospitalization and should be re-evaluated. Patients who are classified as "red" have priority admission to the ICU, followed by those classified as "yellow". Patients classified as "blue/black" remain in conventional hospitalization and receive palliative care with active medical therapy at the discretion of the attending physician and according to the opinion of the patient and/or family. Patients should be re-evaluated on days 2 and 5 and re-classified. Decisions beyond day 5 in icu will depend on the availability of resources (these criteria are those dictated by the Spanish Society of Intensive Care Medicine (Semicyuc) for ICUs).

For the donor:

1. Ability to understand the HIP and sign the IQ of the study.
2. Age equal to or greater than 18 years.

3. Compliance with the criteria to be accepted as a plasma donor according to European and Spanish regulations (RD 1088/2005).
4. Presence of IgG antibodies **against SARS-CoV-2 delectables in peripheral blood 50 UA/mL.**
5. Absence of COVID-19 symptoms in the last 14 days.
6. NEGATIVE SARS-CoV-2 RT-PCR in at least one nasopharyngeal sample.
7. Weight over 50 kg and good venous access.
8. Acceptance for the conservation of serum library samples for the realization of antigranulocyte antibodies; especially in cases in which the recipient presents respiratory clinic.

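### ICU recipient criterion B.7: three of the ten minor items have units that cannot be right as printed, and a fourth carries a sign that contradicts its label (minor)

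*Combined protocol and SAP*

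**What the plan says.** Section 4.2.1 lists the inclusion criteria for ICU recipients as B.1 to B.7. Under B.7, the admission criteria of the Ministry of Health "and the Spanish Society of Intensive Care Medicine will be considered". The text then continues: "A summary is attached to the following table, and more information is added in Annex IX".

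The table has two routes. The first is headed "MAJOR CRITERIA (1 criterion necessary)" and lists septic shock on vasoactive drugs and respiratory failure that needs mechanical ventilation. The second is headed "MINOR CRITERIA (3 or more criteria)" and lists ten items: respiratory rate, PaO2/FiO2, bilateral infiltrates, consciousness, urea, leukopenia with lymphopenia, thrombocytopenia, hypothermia, hypotension and D-dimer.

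The four items at issue read:

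- "Leukopenia (<4000 cells/ml) and lymphopenia"
- "Thrombocytopenia (<100000/ml)"
- "D-dimer > 1 µg/L"
- "Elevation of urea ($< 20", followed by the unit mg/dL

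Table 1 in section 4.3.3 records leukocytes and platelets in x10^9/l, D-dimer in mg/dl and urea in mg/dl.

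**The concern.** B.7 stands among the inclusion criteria, so its limits are decision thresholds and not background. Read literally, the minor route loses two items that nobody can meet and gains one that everybody meets. The urea item, if its sign is as printed, points the wrong way. The rule of three out of ten would then be a different rule from the one intended.

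Version 2.0 makes the trial multicentre. A centre that sees the problem has to substitute its own limits, and a monitor who compares laboratory values with the printed table cannot verify entry by the minor route. What is at stake is a common, checkable definition of who may enter the ICU stratum.

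**Working it through.** The plan gives no figure to reproduce here. The check is unit conversion, a count, and an illustration on assumed prevalences.

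**Printed limits** (B.7 table), converted to the units of Table 1:

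- Leukocytes: 4000 per ml ÷ 1000 = 4 per µl. In litres, 4000 × 10^3 = 4.0 × 10^6 per litre = 0.004 x10^9/l.
- Platelets: 100000 per ml ÷ 1000 = 100 per µl. In litres, 100000 × 10^3 = 1.0 × 10^8 per litre = 0.1 x10^9/l.
- D-dimer: 1 µg/L ÷ 1000 = 0.001 µg/mL = 0.001 mg/L = 0.0001 mg/dl.

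**The same digits in the presumed units** (an assumption; the documents do not state the intended units):

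- Leukocytes: 4000 per µl = 4.0 x10^9/l.
- Platelets: 100000 per µl = 100 x10^9/l.
- D-dimer: 1 µg/mL = 1 mg/L = 0.1 mg/dl.

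Each presumed limit is 1000 times the printed one.

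**Urea.** The label says elevation and the sign says below 20 mg/dL, so the line contradicts itself. Reversing the sign may not settle the limit, because it matters whether urea or urea nitrogen is meant: 20 mg/dL of urea is 20 × 28.02 / 60.06 = 9.3 mg/dL of urea nitrogen.

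**Count.** Two items practically never met (leukocytes, platelets) + one practically always met (D-dimer) + one self-contradictory (urea) + six unaffected = ten.

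**Size, on assumptions.** The documents give no prevalences. I assumed independent items in patients without a major criterion, in the order in which the items are listed above:

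- Low: 0.30, 0.50, 0.70, 0.05, 0.20, 0.05, 0.05, 0.02, 0.05, 0.30
- Middle: 0.50, 0.70, 0.85, 0.10, 0.40, 0.15, 0.10, 0.03, 0.10, 0.50
- High: 0.70, 0.90, 0.95, 0.20, 0.60, 0.25, 0.20, 0.05, 0.20, 0.70

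For the printed table, leukocytes and platelets are set to 0 and D-dimer to 1. Urea is set to 0 or 0.10 (sign taken literally), or left at its intended value (sign a misread). The probability of at least three items is then:

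| Scenario | Intended | Printed, urea 0 | Printed, urea 0.10 | Printed, urea as intended |
|---|---|---|---|---|
| Low | 0.383 | 0.546 | 0.582 | 0.618 |
| Middle | 0.777 | 0.819 | 0.835 | 0.884 |
| High | 0.972 | 0.971 | 0.974 | 0.988 |

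The change in the share of all ICU candidates who satisfy the table is (1 − share with a major criterion) × (printed − intended). The largest change is in the low scenario with urea as intended:

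- Half have a major criterion: 0.50 × (0.618 − 0.383) = 0.12
- 80% have one: 0.20 × 0.235 = 0.05
- 95% have one: 0.05 × 0.235 = 0.01

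The high scenario changes by less than one point throughout. Where there is a visible change, entry becomes looser, because the automatic D-dimer item outweighs the two lost ones.

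**The case against.** The strongest reply is that the table does not control entry. It is a summary of national criteria that are to be considered, and the text points every centre to the issuing societies. Recipients must already be in ICU (B.3) with SOFA > 6 (B.5), and one major criterion suffices. An intensivist will not wait for 4 leukocytes per µl; the item labels make the intended direction plain. All this stands, and it is why the point is minor. It does not make the printed limits right. The available text of Annex IX, to which B.7 refers, deals with notification, arm assignment and the plasma request, and gives no limits.

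The second reply is that the faults may come from the PDF reading. For urea this stands in part: the cell was machine-converted, so the sign may be a misread, although less-than signs elsewhere in the table come through sensibly. For the units it is weak. Three cells would have to be misread, and the µ sign survives in the D-dimer line itself and in the iron row of Table 1. A translation or typing slip is possible, but the limits would still need correcting.

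A reader might infer four certain errors, or that the trial will enrol the wrong ICU patients, or that the arms will differ. The documents do not support these readings. The urea sign is uncertain, no data show who would be affected, and the criteria apply before assignment and to both arms alike.

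**Conclusion.** The point holds as a minor one. Three of the ten minor items have units that are wrong as printed; this follows from arithmetic and basic physiology. The urea item contradicts its label, but only in the text as extracted. The 1000-fold factor assumes that counts per µl and D-dimer in µg/mL were meant.

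The effect on entry is probably small. The range of about 0 to 12 percentage points rests wholly on assumed, independent prevalences, and its upper end needs both uncommon minor items and only half of candidates with a major criterion. Nothing in the sample size or analysis depends on these limits, and no effect on outcomes or on the comparison between arms is shown.

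**What to change.** Correct the table in the next amendment, confirming each limit against the ICU admission criteria that B.7 cites:

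- Leukocytes: < 4.0 x10^9/l, with lymphopenia (Table 1 unit).
- Platelets: < 100 x10^9/l (Table 1 unit).
- D-dimer: presumably > 1 µg/mL, which is > 0.1 mg/dl in the Table 1 unit.
- Urea: a greater-than sign, with the analyte (urea or urea nitrogen) and the limit taken from the cited criteria, not by reversing the sign alone. If the source PDF already shows a greater-than sign, only the analyte and limit need confirming.

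Use the corrected table at every centre. The cost is one check against the cited criteria and up to four table cells. No new data are needed, and the sample and the analysis do not change.

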4.2.2 Exclusion criteria

For the receiver:

A. Recipients hospitalized in COVID-19 plant:

1. Patients with a previous history of allergic reaction to any type of transfusion of blood products.
2. Breastfeeding women or women with pregnancy potential and positive pregnancy test.
3. Patients who have been treated with plasma in the 21 days prior to the screening/baseline visit.
4. Patients who, in the opinion of the researcher, possess any condition that makes the recruitment of the same incompatible.
5. Patients who are at the time of the study, participating in a clinical trial.
6. Patients who have not performed all the procedures in the study.

For the donor:

1. Plasmapheresis in the last 7 days.
2. Blood donation in the last 7 days.
3. Donation of more than 25 L of plasma in the previous 12 months.
4. With the intention of reducing the risk of transfusion-related acute lung injury (LPART/TRALI), only male donors never transfused and women with no history of abortions will be selected.

5. Patients who are at the time of the study, participating in a clinical trial.

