4.3.1. Stages of study and evaluation of the response

a) The study procedures for the patient receiving treatment shall be carried out as follows:

1. Baseline visit/screening:

- Review of inclusion and exclusion criteria: HIP and CI signature.
- Vital signs: Blood pressure, Heart rate, Respiratory rate, Temperature, and oxygen saturation.
- Complete physical examination.

- Review of relevant medical history.
- Rx of Tx
- Electrocardiogram.
- Weight, height, Body mass index.
- ECOG.
- Complete hematology.
- Coagulation study, D-dimer.
- Arterial blood gas.
- Biochemical analysis: Glucose, creatinine, glomerular filtration (CKD-EPI), sodium, potassium, chlorine, or rhea, urate, calcium, ferritin, C-reactive protein, AST, ALT, GGT, FA, LDH, CPK, troponin, procalcitonin.
- Inflammatory parameters: IL-6.
- Serology HIV, HVC, HVB, SYPHILIS.
- Imaging tests according to usual practice.
- Real Time-PCR for detection of Coronavirus SARS-COV-2 in nasal smear and pharynx.
- Quantitative determination of antibodies (IgG, IgM) against Coronavirus SARS-COV-2.
- Immunohematological study (ABO Group, Rh, Indirect Coombs).
- Concomitant medication evaluation.

2. Treatment initiation visit (First dose: day 1): Marked procedures (*) do not need to be repeated if performed at baseline in the previous 7 days:

- Study treatment assignment: if it is an intervention group, first plasma infusion.
- Vital signs (TA, FC, FR, T^a) pre-infusion and post-infusion*.
- Complete physical examination*.
- ECOG*.
- Hematology*.
- Biochemical analysis*.
- Inflammatory parameters*.
- Concomitant medication evaluation.
- Evaluation of emerging adverse effects.

3. Visit of Day 2:

- if it is an intervention group, second plasma infusion.
- Concomitant medication evaluation.
- Evaluation of emerging adverse effects.

4. Visit of Day 3:

- Vital signs (TA, FC, FR, T^a).

- Physical examination.
- ECOG.
- Hematimetry.
- Biochemical analysis.
- Inflammatory parameters.
- Nasal and pharyngeal smear for RT-PCR of Coronavirus SARS-COV-2.
- Quantitative determination of antibodies (IgG, IgM) against Coronavirus SARS-COV-2.
- Concomitant medication evaluation.
- Evaluation of emerging adverse effects.
- Clinical/virological response evaluation.

5. Visit of Day 7:

- Vital signs (TA, FC, FR, T^a).
- Physical examination.
- ECOG.
- Hematimetry.
- Biochemical analysis.
- Inflammatory parameters.
- ECG.
- Nasal and pharyngeal smear for RT-PCR of Coronavirus SARS-COV-2

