- Quantitative determination of antibodies (IgG, IgM) against Coronavirus SARS-COV-2.
- Concomitant medication evaluation
- Evaluation of emerging adverse effects.
- Clinical/virological response evaluation.

6. Visit of Day 14:

- Vital signs (TA, FC, FR, T^a).
- Physical examination.
- Hematimetry.
- Biochemical analysis.
- Nasal and pharyngeal smear for RT-PCR of Coronavirus SARS-COV-2.
- Quantitative determination of antibodies (IgG, IgM) against Coronavirus SARS-COV-2.
- Concomitant medication evaluation.
- Evaluation of emerging adverse effects.
- Clinical/virological response evaluation.

7. Visit of Day 21/end of study (at discharge):

- Vital signs (TA, FC, FR, T^a).
- Physical examination.

- Rx of Tx to assess evolution/resolution of infiltrates.
- ECG.
- ECOG.
- Hematimetry.
- Biochemical analysis.
- Inflammatory parameters.
- Real Time-PCR for SARS-COV-2 viral load study.
- Quantitative determination of antibodies (IgG, IgM) against Coronavirus SARS-COV-2.
- Concomitant medication evaluation.
- Evaluation of emerging adverse effects.
- Clinical/virological response evaluation.

IMPORTANT: In cases where the patient is discharged after 7 days, visits on day 14 and day 21 can be made on an outpatient basis, in outpatient consultations or day hospital, after appointment with the patient.

Screening visits and day 1 may overlap on the same date threaten life the inclusion criteria are confirmed and none of the exclusion is met.

There will be a margin of +/- 24 hours to perform the procedures of visits 7, 14 and 21 (to be able to adjust the appointments in external consultation).

The study procedures for study subjects (control and treatment groups) can be reviewed in summary form in the following table:

Procedure	Study days						
	Screening/ Basal	Day 1*	Day 2	Day 3	Day 7	Day 14	Day 21
DATE							
Signature of informed consent	X						
Medical history review	X						
Physical examination	X	X*		X	X	X	X
Vitals signs	X	X*		X	X	X	X
Weight, Height, BMI	X						
ECOG	X	X*		X	X	X	X
ECG	X				X		X
ABO/Rh Group	X						
Hematimetry	X	X*		X	X	X	X
Coagulation	X	X*		X	X	X	X
Biochemistry	X	X*		X	X	X	X
Study of inflammatory parameters	X			X	X		X
Serology Important IgG/IgM anti-COVID	X			x	x	x	x
Quantitative titration antibodies	X			X	X	X	X
COVID PCR	X			X	X	X	X
Chest Rx	x						x
AE Review	X	X	X	X	X	X	X
Concomitant review	X	X	X	X	X	X	X
Clinical response	X			X	X	X	X
PLASMA TRANSFUSION		X	X				

Table 3. Summary of procedures in the study subjects.

LEGEND:

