4.3.2. Duration of the study

In version 1.0 of the study, the estimated study duration period was 3 months from the date of compliance with the Clinical Research Ethics Committee (in Spain CEIm) Research Ethics Committee (CEIm) and Spanish Agency for Medicines and Health Products (in Spain AEMPS). In this version 2.0 the study period is extended to recruit a sufficient n to be able to estimate the effectiveness of the treatment or failing that until the competent authorities so determine. The follow-up period for patients will be 21 days from the start date of the study and if necessary, it will be extended as long as necessary, in order to ensure patient safety.

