		2	Past infection
		3	Immunized
		4	Negative
CMV Serology		0	Negative
		1	Positive
Syphilis Serology		0	Negative
		1	Positive
INMHEMATOLOGIC STUDY			
ABO Blood Group		0	A
		1	B
		2	AB
		3	O
Rh		0	Present
		1	Absent
Irregular Blood Group antibodies		0	Negative
		1	Positive
DIAGNOSTIC/MICROBIOLOGICAL PROCEDURES			
Quantitative titration of SARS-COV2 antibodies (IgG/IgM)		UA/mL	Number
RT-PCR SARS-COV-2		0	Negative
		1	Positive

Time to RT-PCR negativization	Days		Number
CLINICAL CRITERIA			
Pleural effusion		0	Negative
		1	Positive
PSI score		1	Valuation not required
		2	<=70
		3	71 - 90
		4	91 - 130
		5	>130
WHO Progression Scale		0	Uninfected; no viral RNA detection.
		1	Asymptomatic; viral RNA detection
		2	Symptomatic. Independent
		3	Symptomatic. Need for assistance
		4	Hospitalized. Oxygen-free
		5	Hospitalized. Oxygen with mask or nasal tips
		6	Hospitalized. Oxygen by non-invasive ventilation (NIV) or high flow.
		7	Intubation or mechanical ventilation. PO2/FIO2>= 150; or SpO2/FO2> 200
		8	Mechanical ventilation (pO2/FIO2< 150, or SpO2/FIO2< 200), or vasopressor (norepinephrine >0.3 microg/Kg/min)
		9	Mechanical ventilation (pO2/FIO2< 150, or SpO2/FIO2< 200), or vasopressor (norepinephrine >0.3 microg/Kg/min) o dialysis o ECMO
% of patients requiring ICU admission			Number
15-day mortality rate			Number
Mortality rate at 30 days			Number
Days of hospitalization			Number
SECURITY CRITERIA			
Emerging adverse effects (ASD) \geq GIII		0	No
		1	Yes
Type TEAE SPECIFY			Name
Cumulative rate/incidence of ASD \geq GIII in experimental branch			Number

Cumulative rate/incidence of emerging adverse events (ASD) any grade in experimental branch			Number
Hospital discharge date			Date
Exitus		0	Yes
		1	No

Table 1. Variables that will be included in the database of the study.

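### Ward exclusion criterion 6 cannot be judged at screening; applied literally after assignment, it would remove early deaths and incomplete patients, and no analysis set prevents this

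*Combined protocol and SAP*

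**What the plan says.** The recipient exclusion list in section 4.2.2 has one heading, "A. Recipients hospitalized in COVID-19 plant", and its sixth item is "Patients who have not performed all the procedures in the study". The item is not limited to screening procedures or to one arm. No exclusion list for ICU recipients follows.

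Other parts of the protocol bear on it:

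- **Prospective compliance (4.2.1).** Ward inclusion criterion 7, repeated as ICU criterion 6, is "Accept the condition of complying with the procedures established in the protocol".
- **Timing (4.3.1).** The inclusion and exclusion criteria are reviewed at the baseline/screening visit. The day-1 visit then contains "Study treatment assignment: if it is an intervention group, first plasma infusion".
- **Length and arms (4.3.1, 4.3.2).** The last visit is headed "7. Visit of Day 21/end of study (at discharge)". The schedule covers both arms: "The study procedures for study subjects (control and treatment groups) can be reviewed in summary form in the following table". Section 4.3.2 adds: "The follow-up period for patients will be 21 days from the start date of the study".
- **Outcomes (4.3.3, Table 1).** The variables include "15-day mortality rate", the 30-day rate, and death as a yes/no item.
- **Removal (4.2.3).** The list of reasons for leaving the study includes not having had both infusions, death, and completing the study. Missed visits or tests are not on it.
- **Analysis (5).** No analysis set is defined, and no rule is given for deaths or missing visits.

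**The concern.** An eligibility criterion has to be decidable before assignment. Whether a patient has had every study procedure is known only at the end of follow-up, so the line can have an effect only by reaching back to patients who already have an arm.

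Used that way, it would select on what happened after assignment. Death before day 21, early recovery without return, and a missed swab would all lead to exclusion, and each may depend on the arm. The trial is open label, so staff and patients know the arm when attendance and completeness are decided. The retained groups would no longer be the groups that were assigned, and the mortality variables would lose the events they are meant to count.

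**Working it through.** The plan gives no sample size, event rate, attendance rate or dropout rate, so there is no figure of its own to reproduce. The check is a reading of the passages against each other, followed by illustrations on assumed inputs.

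**1. The criterion at the baseline review.** Assignment is on day 1; the scheduled assessments follow on days 3, 7, 14 and 21. At screening no candidate has done them. Taken literally at that moment, the criterion excludes everyone, so it cannot be meant literally there.

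**2. The criterion as willingness to comply.** Ward inclusion criterion 7 already requires this, and ward criterion 8 requires an expected stay of at least 5 days so that procedures can be done. On this reading the line adds nothing.

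**3. The criterion after assignment.** A patient who dies before the day-21 visit cannot have had all procedures. The visit window is plus or minus 24 hours, so the scheduled last visit falls on day 20 at the earliest. Every death by day 15 precedes it. (The visit heading also mentions discharge, but section 4.3.1 provides outpatient visits on days 14 and 21 for patients already discharged, so day 21 is taken as the end.)

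Among retained ward patients, 15-day mortality would therefore be 0% in both arms whatever the true rates. For example, an assumed 20% control against 10% plasma would become 0% against 0%. The 30-day rate could count only deaths after the last visit. This cannot stand beside Table 1 in section 4.3.3.

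**4. What counts as all procedures.** Table 3 marks ECOG and coagulation on day 14; the written list for that visit has neither. The condition has no single definition, so applying it would need judgement made with knowledge of the arm.

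**5. Completeness among survivors (assumed attendance).** With probability *a* of attending each of the four visits, independent between visits, the share retained is *a*⁴:

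- 0.95⁴ = 0.81
- 0.90⁴ = 0.66

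**6. Direction of a possible bias (assumed rates).** Let *r* be the proportion of assigned patients alive and recovered at day 21, and *d* the proportion dying earlier. With no other incompleteness, the rate among completers is *r* / (1 − *d*).

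| | Control | Plasma |
|---|---|---|
| *r* | 70% | 70% |
| *d* | 10% | 20% |
| Completers | 70/90 = 77.8% | 70/80 = 87.5% |

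The arm with twice the early deaths appears 9.7 points better, although the assigned groups do equally well on this outcome. If *d* is 15% in both arms, both show 70/85 = 82.4% and this distortion vanishes.

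**The case against.** The strongest reply is that the criterion was never meant to act after assignment. Section 4.3.1 places the exclusion review at screening and lets screening coincide with day 1 only if no exclusion is met. A natural intention would be that required baseline tests had not been done. The document reads as a rough translation, so a verb tense is weak evidence. This stands as an account of intent, and it is why one of the acceptable fixes is to limit the line to screening procedures. It does not make the present text usable, because the text says all procedures in the study.

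A reader might infer more than the documents support:

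- **That the plan drops early deaths from the analysis.** No passage says so. Section 4.2.3 lists death next to completing the study, so removal there can simply mean the end of participation, and Table 1 collects mortality. What is shown is a contradiction with nothing in section 5 to resolve it.
- **That anyone who dies, in any unit, is excluded.** The line stands under the ward heading; its use in ICU recipients is unstated. Deaths after the day-21 visit are unaffected.
- **That the different ward and ICU rules come from this line.** The whole recipient exclusion list has only a ward heading, so deleting one item does not cure that.
- **That almost nobody would qualify.** Table 3 has 54 marks on days 3, 7, 14 and 21, and compounding a small miss rate over them gives a dramatic loss. Marks within one visit are not independent, and the table and visit lists disagree, so that calculation is not used. The visit-level figures are milder but are also assumptions.

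**Conclusion.** The criterion is wrong as written. At the baseline review it is either impossible to meet or, read as willingness, redundant. Applied literally after assignment, it becomes a completer rule for ward patients in both arms that contradicts the trial's own mortality variables, and section 5 contains nothing to prevent that use.

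The consequence is conditional on the literal, post-assignment reading. Under it, recorded 15-day mortality in the ward set is zero in both arms, and other comparisons are among survivors with complete data. The size of any bias cannot be derived from the documents: the 81% and 66% retention rest on assumed attendance, and the 9.7-point reversal on assumed recovery and death rates that differ between arms in the way shown.

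**What to change.** 1. Delete criterion 6 from the ward exclusion list, or limit it expressly to screening procedures that must be completed before assignment. Ward inclusion criterion 7 and ICU criterion 6 remain as the prospective compliance condition.
2. State in section 5 that all assigned patients are analysed in their assigned arm, that a missed procedure or visit is a recorded deviation, and that death before a visit is an outcome.
3. Reconcile this with section 4.2.3, so that leaving study procedures for any listed reason, including not having had both infusions, does not remove a patient's outcome data.

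The cost is one deleted or reworded line and a few sentences in an amendment. The downside is that some later laboratory values will be missing for retained patients, and section 5 will have to say how they are handled.
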